## CONFIDENTIAL

If the patient is administered a COVID-19 vaccination during the AST-VAC2 vaccination period, there should be a 48 hours interval between the two vaccinations and they should be administered to different sites. The AST-VAC2 vaccination should be delayed as needed to accommodate this interval.

If the patient is withdrawn from further trial treatment, follow up information and post vaccination research blood [REDACTED] sampling will still be applicable unless the patient withdraws consent from further follow up and participation in the trial or if the Sponsor advises that further sampling is not required.

### 5.4 Duration of treatment

Treatment should continue so that the patient receives six vaccinations unless (a) the patient asks to be withdrawn, (b) there is evidence of disease progression (as per Immune-Related Response Criteria (irRC) given in [Appendix 3](#)), (c) the patient is experiencing unacceptable toxicity or (d) the investigator feels the patient should stop the vaccinations for any other reason. Other reasons are listed in [Section 11.0](#).

An End of Vaccination visit will be carried out 30 days post the last vaccination day. This visit will document any emerging AEs since the last vaccination. Adverse events present at this visit, attributed to AST-VAC2 (highly probably, probably or possibly related) will be followed up until resolution or stabilisation of these events (even if the patient starts another anti-tumour treatment).

If a patient terminates treatment prematurely, an End of Vaccination visit should be performed within 30 days of the last vaccination day or when the decision is taken to withdraw the patient from further vaccinations or the trial. These patients should also be asked to continue attending hospital for the 3, 6 and 12 month from first vaccination follow-up visits to provide blood samples for immune analysis (unless the patient withdraws consent from further follow up and participation in the trial or if the Sponsor advises that further sampling is not required).

Patients will be asked to attend follow up as per Section 7.4 until the end of trial (EoT) is declared. The 'End of Trial' will be declared when all patients have either withdrawn (see [Section 11.0](#)) from the trial or died, or the last patient has completed their final follow-up visit (5 years post the first vaccination), whichever is the latter.

#### 5.4.1 Replacement of patients

Three administrations of AST-VAC1 (i.e. three complete doses) have previously been shown to demonstrate the first indications of an immune response therefore patients who receive fewer than three AST-VAC2 vaccinations (for reasons other than toxicity) will be replaced, pending vaccine availability.

### 5.5 Concomitant medication and treatment

Concomitant medication may be given as medically indicated. Details (including name, indication for use and start and stop dates) of the concomitant medication given must be recorded in the patient's medical records and details entered into the eCRF.

The patient must not receive other anti-cancer therapy or investigational drugs during the vaccination phase of the trial. Following the vaccination period, if other treatment is received during the follow up period, this should be documented accordingly however, follow up information (including AEs related to AST-VAC2) should still be collected as per protocol, [Section 7.4](#).

Use of immunosuppressive medication, including corticosteroids (other than replacement dosing for adrenal insufficiency/pituitary failure), is excluded in this protocol. Inhaled and topical steroids are permitted. A short course of systemic steroids may be permitted for management of adverse events, however, this should be discussed and agreed in advance by the CDD Medical Advisor and/or the Chief Investigator.

Patients may be administered a COVID-19 vaccine during the trial (including during screening), at the discretion of the Investigator. Where possible, the COVID-19 vaccination should be administered before

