### 7.4 Follow-up

#### 7.4.1 3, 6, 9 and 12 months post first vaccination

##### Patients should undergo the following assessments:

- Research blood samples 3, 6 and 12 months (all +/-1 week) post the first vaccination.
- At the above time points, an evaluation of any AST-VAC2 related AEs will also be performed. Assessments can be performed as clinically indicated.
- A further AE evaluation should be performed at 9 months post the first vaccination also. This can be in the form of a phone call to the patient.
- Any concomitant medications relevant to AST-VAC2-related AEs should be recorded.

All new and ongoing AST-VAC2-related AEs should be followed up until resolution or stabilisation, even if the patient goes onto another anti-cancer treatment. SAEs considered related to AST-VAC2 are always reportable regardless of the time elapsed.

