5.13.2 Secondary endpoints

5.13.2.1 Identification of peptide specific T cells (Secondary Immunogenicity Endpoint Population)

Immunological response will be measured in whole blood (PBMCs) by hTERT specific T cells as measured by ELISPOT analysis at the following time points:

- baseline,
- vaccination weeks 3, 4 and 6,
- 2 weeks post last vaccination and
- 3, 6 and 12 months post first vaccination.

Vaccine induced ELISPOT response in blood will be reported longitudinally for each patient. The total number of patients showing durable peripheral immune response, defined as a change in one validated assay at two time points after at least two vaccinations (where a change is defined as 2.5 fold change over baseline [after removal of background], assay control and >35 spots/ 10^6 cells) will be reported.

Interim reports are expected at timepoints to be agreed between the Sponsor and the laboratory. Interim reports will be provided within one month of completing the agreed patient analyses. A final report is expected no more than 10 weeks after the last sample is analysed.

The data will be reported in tables and graphs/figures. No formal statistical analysis is planned. The results will be summarised in the CSR and the final report included as an appendix.

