6. TABLE LISTINGS AND FIGURES

6.1 LISTINGS

CSR Appendix Subsection	CSR Listing Number	Listing	New Listing Name for CSR
16.2.1 Discontinued Patients	16.2.1.1	Vaccine Received	Vaccine Received
	16.2.1.2	End of Vaccination	Vaccination Completion
16.2.2 Protocol Deviations	16.2.2.1	To be provided from the central deviation tracker	N/A
16.2.3 Patients excluded from Efficacy Analysis	16.2.3.1	Enrolment	Enrolled Patients
16.2.4 Demographic and Baseline Data	16.2.4.1	Demographics	Patient Demography
	16.2.4.2	Diagnosis	Diagnosis of Primary Disease
	16.2.4.3	Medical History	Medical History
	16.2.4.4	Medical Procedures	Medical Procedures
	16.2.4.5	Prior and Concomitant Medications	Prior and Concomitant Medications
	16.2.4.6.1	Surgery	Previous Treatment for Malignant Disease - Surgery
	16.2.4.6.2	Chemotherapy/other therapy	Previous Treatment for Malignant Disease – Chemotherapy/Other Therapy
	16.2.4.6.3	Radiotherapy	Previous Treatment for Malignant Disease - Radiotherapy
	16.2.4.7	Physical Examination	Physical Examination
	16.2.4.8	Chest X-ray Results	Chest X-ray
16.2.5 Compliance and Drug Administration	16.2.5.1	Drug Administration - Vaccination	Drug Administration - Vaccination
16.2.6 Efficacy Response	16.2.6.1	Immune Response Index Lesions	Immune Response Index Lesions
	16.2.6.2	Immune Response Non-Index Lesions	Immune Response Non-Index Lesions
	16.2.6.3	Immune Related Response Criteria	Immune Related Response
	16.2.6.4	New Anti-Cancer Therapy	New Anti-Cancer Therapy
	16.2.6.5	Survival	Survival
	16.2.6.9	CEA Sample	CEA Sample
16.2.7 Safety	16.2.7.1	Adverse Events	Adverse Events

	16.2.7.2	Adverse Events by SOC	Adverse Events by SOC
	16.2.7.3	Follow-Up	Follow Up
	16.2.7.4	WHO	WHO Performance Status
	16.2.7.5	Haematology	Haematology: Haemoglobin, WBC, Neutrophils, Lymphocytes, Eosinophils, Platelets
	16.2.7.6	Biochemistry	Biochemistry: Sodium, Potassium, Adjusted calcium, Phosphate, Urea, Creatinine, Total Protein, Albumin, Bilirubin, ALP, ALT, AST, CRP
	16.2.7.7	Urinalysis	Urinalysis: Glucose, Protein, Blood, pH
	16.2.7.8	Vital Signs	Vital Signs
	16.2.7.9	Pregnancy	Pregnancy
	16.2.7.10	ECG	ECG

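### The durable-response count and the 3-, 6- and 12-month mean fold changes admit ELISPOT samples taken after a new anti-cancer therapy, with no visible rule to separate them

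*Protocol*

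**What the plan says.** Protocol 5.5 limits the ban to one period: "The patient must not receive other anti-cancer therapy or investigational drugs during the vaccination phase of the trial". For the time afterwards it states: "Following the vaccination period, if other treatment is received during the follow up period, this should be documented accordingly". Follow-up then continues under Protocol 7.4, where 7.4.1 schedules "Research blood samples 3, 6 and 12 months (all +/-1 week) post the first vaccination". Protocol 5.4 asks patients who stop vaccination early, progression being one listed reason, to attend for the same three samples.

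SAP 5.13.2.1 labels the result as the vaccine's: "Vaccine induced ELISPOT response in blood will be reported longitudinally for each patient". A durable response is "defined as a change in one validated assay at two time points after at least two vaccinations". The threshold reads "where a change is defined as 2.5 fold change over baseline [after removal of background], assay control and" more than 35 spots per 10^6 cells. The listed time points include "3, 6 and 12 months post first vaccination".

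No visible text makes a sample's use depend on new therapy. This holds for the immunogenicity population (Protocol 3.4.3, SAP 4.1), the analysis (SAP 5.13.2.1) and the results tables (SAP 7.5.3 and 7.5.4). The Undetermined row in SAP 7.5.3 covers only a failed baseline sample or too few time points. The SAP does deal with later therapy for survival, which is assessed whether or not it is given (4.1 and 5.9), and it plans a listing titled "New Anti-Cancer Therapy" (6.1) without linking that to ELISPOT.

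**The concern.** The objective is the immunogenicity of AST-VAC2, but the late samples may reflect the vaccine, a later treatment, or both. All enrolled patients receive the vaccine (Protocol 1.4), so there is no comparison group to show what later treatment does alone. The bias could run either way.

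Two outputs are exposed: the durable-responder count (Outcome Measure 3) and the 3-, 6- and 12-month mean fold changes (Outcome Measure 4), which would pool patients on and off new therapy. Protocol 13 names durable immune response as a factor in further development, so the count should have one clear meaning even though it is descriptive.

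**Working it through.** The plan gives no sample-size or power figure for this endpoint, so there is none to reproduce. The checks below cover the number of samples, their timing, the pairs that can qualify, and the weight of one patient.

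**Number of samples.** Protocol 8.3.1.1 takes 72 mL at baseline and 48 mL at each later point, about 408 mL in total. 72 + 7 × 48 = 408, so there are 7 post-baseline samples: weeks 3, 4 and 6, 2 weeks after the last vaccination, and 3, 6 and 12 months.

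**Timing.** Take the first vaccination as day 0, with no delays.
- Last vaccination: 5 × 7 = day 35.
- 2-week sample: 35 + 14 = day 49.
- End of Vaccination visit: 35 + 30 ± 5 = days 60 to 70. The entry criterion in Protocol 4.1.1 asks only for a judgement that no other treatment will be needed up to this visit.
- 3-month sample: about 91 ± 7 = days 84 to 98.

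The 3-, 6- and 12-month samples therefore fall after both the ban and the period in which no other treatment is expected. The 2-week sample lies outside the ban but inside the second period.

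**Qualifying pairs.** The rule needs two samples, and all 7 qualify (the week 3 sample precedes the third vaccination).
- All pairs: C(7,2) = 21.
- Pairs using only weeks 3, 4, 6 and the 2-week sample: C(4,2) = 6.
- Pairs using at least one late sample: 21 − 6 = 15.
- Pairs using only late samples: C(3,2) = 3.
- If the 2-week sample is also treated as exposed: 21 − C(3,2) = 18, and C(4,2) = 6.

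**Early stopper.** A patient who stops after three vaccinations meets the vaccination minimum for immune evaluability. Five samples remain (week 3, 2-week, 3, 6 and 12 months), giving C(5,2) = 10 pairs. Only C(2,2) = 1 avoids the late samples, so 9 of 10 use one.

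**Weight of one patient.** Protocol 1.6 allows up to eight patients: 1/8 = 12.5 points. If 6 are evaluable, which is an assumption: 1/6 = 16.7 points. As an illustration, losing one responder of three at n=8 moves 3/8 = 37.5% (exact 95% interval 8.5 to 75.5) to 2/8 = 25.0% (3.2 to 65.1).

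**Chance of a wrong credit.** The documents give no inputs, so only an assumed range is possible. Suppose m of 8 patients start new therapy and each has probability q of a treatment-caused response that meets the rule. The chance of at least one wrong credit is 1 − (1 − q)^m. With m=1 and q=0.05 it is 5%; with m=4 and q=0.30 it is 1 − 0.70^4 = 76%. A range this wide shows that the documents cannot settle the size of the bias.

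**The case against.** - **Patients with early responses are unaffected.** Two positives among weeks 3, 4, 6 and the 2-week sample make a patient durable whatever follows. Status can change only for a patient with at most one early positive, and 12 of the 15 exposed pairs also need an early positive. This stands (subject to the caveat above about the 2-week sample), and it is why the pair count is not a risk.
- **The protocol has a partial safeguard.** Under 3.4.3 and 8.3.1, later samples may be left unanalysed when the 3-month result is negative. That covers some patients who would qualify only on 6- and 12-month samples. It is optional, and the 3-month sample can itself follow new therapy, so it limits the problem only in part.
- **Entry is for patients without suitable alternatives.** This makes early switching less likely. Yet Protocol 5.5 and 7.4.3 and SAP 4.1, 5.9 and 6.1 all provide for later therapy.
- **A reader could check by hand.** Results are reported per patient, the laboratory report is appended to the clinical study report, and new therapy is listed. The headline count and the registry tables carry no flag, however, and the ELISPOT data sit outside the clinical database (SAP 5.13), so the link has to be planned.
- **Redaction.** Blacked-out text follows the immunogenicity population in SAP 4.1 and the evaluability criteria in Protocol 3.4.3. A rule there cannot be excluded.
- **No formal analysis is planned.** True, but a descriptive count still needs a definition that matches its label.

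**Conclusion.** The point holds conditionally. As visibly written, the rule counts samples taken after a new anti-cancer therapy. If that therapy changed the ELISPOT result, the change would be credited to AST-VAC2 or could hide a vaccine response. The exposure is 3 of 7 samples, 15 of 21 pairs with at least one late sample, and 3 with only late samples. Each reclassified patient is worth 12.5 points at n=8, or 16.7 if 6 are evaluable. These figures assume the full schedule without delays and no relevant rule under the redactions.

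A reader might infer three stronger things that the documents do not support.
- That later treatment will in fact produce false responders: no rate of new therapy, or of its effect on hTERT-specific T cells, is given.
- That 15 of 21 is the chance of misclassification: the pairs are not equally likely, and most cannot change a patient's status without an early positive.
- That the same flag should cover systemic steroids: Protocol 5.5 already restricts them, and follow-up records only medication relevant to vaccine-related adverse events (Protocol 7.4.1; 7.5, note n), so other courses may not be captured.

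**What to change.** In SAP 5.13.2.1 and Outcome Measures 3 and 4, keep the main analysis and add the following.
1. Flag each ELISPOT sample as before or after the start of the first new anti-cancer therapy, using the recorded treatment data.
2. Mark that start date on the per-patient longitudinal plots.
3. Report the durable-responder count and the mean fold change, with N at each time point, a second time using only samples before new therapy.

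Dosing and sampling do not change. The costs and limits should be stated with the result.
- Laboratory data must be merged with eCRF dates. The SAP gives only the listing's title, so confirm that it holds a start date; Protocol 7.4.3 collects post-trial treatment only where known.
- Outcome Measure 3 needs a second count. Outcome Measure 4 needs further N and mean entries at 3, 6 and 12 months, and at 2 weeks if any patient has started new therapy by then.
- The second analysis has fewer samples, and the restricted set may favour patients who did not progress. It should sit beside the main result as a check, not replace it.

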**CONFIDENTIAL**

trial entry or after completion of the AST-VAC2 vaccination period. However, if the COVID-19 vaccination is to be administered during the AST-VAC2 vaccination period, there should be an interval of 48 hours between administration of the two vaccines and they should be administered to different sites. Details of the COVID-19 vaccination should be recorded in the medical records and details entered in the eCRF.

## 6 PHARMACEUTICAL INFORMATION

### 6.1 Supply of AST-VAC2 vaccine

A complete certificate of analysis and a Qualified Person (QP) certification must be provided with each batch of the AST-VAC2.

For information on AST-VAC2 and re-ordering of supplies, contact the Clinical Research Associate (CRA)/Clinical Study Manager (CSM) responsible for the trial who will arrange further supplies.

AST-VAC2 will be supplied by:

The Cancer Research UK Biotherapeutics Development Unit (BDU) must send a copy of the drug shipment form to the CSM/CRA following despatch of AST-VAC2.

The primary and secondary packaging for AST-VAC2 will be labelled according to Eudralex Volume 4: Annex 13 'Investigational Medicinal Products' of the European Union guide to Good Manufacturing Practice (GMP).

Prior to despatch of AST-VAC2 to the clinical trial site, a label detailing the investigator name and investigator site name will be added to the secondary packaging (where applicable) at the manufacturing authorisation holder (MIA) (IMP) licensed manufacturer in accordance with GMP.

An example of the approved label(s) can be found in the Trial Master File (TMF) and site Pharmacy File.

### 6.2 Pharmaceutical data

#### 6.2.1 Formulation of AST-VAC2

#### 6.2.2 Storage conditions

All supplies must be stored in a secure, limited access storage area. AST-VAC2 must be stored at  $\leq -140^{\circ}\text{C}$  in the vapour phase of a liquid nitrogen tank. The storage temperature must be fully monitored at all times.

#### 6.2.3 Method of dilution/reconstitution of AST-VAC2

There is no reconstitution or dilution of the product required. The IMP should be administered to the patient within a maximum of two hours following removal from storage and thaw. Instructions on thawing and loading the syringe will be supplied to sites.

#### 6.2.4 Stability and labelling of the AST-VAC2

The prepared solution for administration has a maximum time period of two hours from removal from storage, thawing and administration to patient. Product should be stored in a cooled container post thawing during this time. Ideally administration should occur as soon as possible after thaw and within two hours maximum

## CONFIDENTIAL

The product is supplied in Crystal Zenith (CZ) vials packed into a CZ box containing six individual doses and must not be removed from the primary packaging until time of administration. It must not be placed in any other container.

Labelling requirements for the AST-VAC2 must include the following information:

- Cancer Research UK,
- AST-VAC2,
- Batch XXX.XX.XX,
- For Intra-Dermal admin,
- Protocol No CRUKD/17/003,
- 0.6 mL at  $2.0 \times 10^7$  cells/vial

Expiry date will not be detailed on the vial but will be shown on the secondary packaging (CZ boxes).

The actual cell dose patients may receive will vary, up to a maximum of  $2 \times 10^7$  viable cells, to achieve a target dose of  $1 \times 10^7$  viable cells - please see Section 6.2.5.

### 6.2.5 AST-VAC2 administration

Before administering the AST-VAC2 vaccine, the exact dosage must always be double-checked by a second suitably qualified person at site. All checks and double-checks must be documented (signed and dated) and the documentation must be available for the CRA/CSM to verify.

Each weekly AST-VAC2 vaccine dose will be administered as a split dose via two id injections at a target dose defined as  $1 \times 10^7$  viable cells. Each vial of AST-VAC2 will be filled at a concentration of  $2 \times 10^7$  viable cells per vial (pre-cryopreservation) and the release specification for the product strength has been set at  $\geq 1 \times 10^7$  viable cells/vial post thawing (based on stability data). The actual cell dose patients may receive will vary, up to a maximum of  $2 \times 10^7$  viable cells, to achieve a target dose of  $1 \times 10^7$  viable cells. There is no dose escalation planned during CRUKD/17/003.

Each vial of AST-VAC2 will contain 0.6 mL. For each vaccination, vial contents should be drawn into one needle from the vial and delivered as two separate id injections. Each injection will be a maximum of 0.3 mL each. The injections should be administered to the same body site approximately 1 cm apart.

Patients should receive the id injections in either the deltoid muscle on the arm, the outer thigh surface, anterior abdominal wall or buttock. If an injection site reaction (ISR) has resolved after the first vaccination day/previous vaccination days then for subsequent injections, injections can be administered at the same body site. If an ISR from a previous vaccination is still present ( $\geq$ Grade 1) then the injection should be administered into an alternative site. The site of injection will be documented for each vaccination.

If a patient is administered a COVID-19 vaccination during the AST-VAC2 vaccination period, there should be an interval of 48 hours between the administration of the vaccines and they should be administered to different sites.

### 6.2.6 Vein extravasation/accidental spillages

As AST-VAC2 is administered intradermally, vein extravasation should not be a potential risk. Accidental spillages should be dealt with according to hospital policy.

### 6.3 AST-VAC2 accountability

Accurate records of all AST-VAC2 shipments and vials dispensed must be maintained in the local pharmacy. Once the product is thawed the injection must be administered within two hours. If this cannot occur, the product cannot be re-frozen and must be disposed of as per hospital policy. This must be noted on the inventory for authorisation by CRA/ CSM. This inventory record must be available for inspection at any time by CRAs or CSMs of the Sponsor. AST-VAC2 supplies are to be used only in accordance with this protocol and under the supervision of the Investigator.

## CONFIDENTIAL

Unused product (thawed or frozen) should be returned to pharmacy for destruction. The Investigator undertakes not to destroy any unused or returned AST-VAC2 unless authorised to do so by the Sponsor. Any unused AST-VAC2 must be destroyed according to hospital procedures and properly accounted for using the IMP Destruction Form and also on the IMP Accountability Record. During the course of the trial the CRA will check the numbers of vials of AST-VAC2 shipped to the centre, the number used and the number destroyed. The pharmacy will give an account of any discrepancy.

